9 INVESTIGATIONAL PLAN

9.1 Overall Study Design and Plan

9.1.1 Description

This is a randomized, double-blinded, placebo-controlled, 2-arm study, with an open-label extension period following double-blind treatment, to investigate the anti-pruritic efficacy and safety of NAL ER tablets. Eligible subjects will be randomized to NAL ER (2-week titration followed by 162 mg BID for 12 weeks) or matching placebo (14 weeks duration), with the primary endpoint evaluation at Week 14. If permanent discontinuation of investigational product occurs anytime between Day 1 and the Week 14 visit, the subject must be asked to complete the Off-Treatment visit, the Last Visit, the End of Study telephone call, and to return to the clinic for the study planned Week 14 visit (unless consent is withdrawn). During the open-label extension, subjects who received NAL ER will continue on NAL ER for a total of 38 additional weeks (total treatment duration 52 weeks including titration) and subjects who received placebo will

crossover to NAL ER for a total of 38 weeks (including titration). Upon discontinuation of investigational product, all subjects will complete the 2-week off-treatment and safety follow-up period, regardless of when and why the subject discontinued study treatment, unless they withdraw consent. In addition, a final follow-up itch and safety assessment will be made via the End of Study telephone call 4 weeks after the last dose of investigational product. The total planned study duration from randomization through to the last telephone contact is 56 weeks.

Approximately 360 subjects with diagnosed PN will be randomized (1:1) to one of the following treatment arms:

Arm 1: Blinded active titration over 2 weeks (to achieve a final NAL ER dose of 162 mg) followed by 162 mg BID for 12 weeks with continuation into the extension titration period (blinded), and the open-label fixed-dose period, followed by a 2-week off-treatment safety follow-up period and a final telephone contact, for itch and safety assessment, 4 weeks after investigational product discontinuation.

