5. SAMPLE SIZE AND POWER

The planned sample size of approximately 240 subjects (120 per group) is based on assumed responder percentages for placebo and NAL ER of 25% and 45%, respectively. These responder percentages represent estimates based on the Week 10 data from the TR03 study. Power is set at 90% with a 2-sided significance level of 0.05.

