5.2 Calculations

Approximately 30 - 45 sites are expected to participate in the current study. In SAS PROC POWER, the LOGISTIC setting was used to approximate the power for a chi-square test comparing the 2 treatment groups with respect to response, without site in the model, and a CMH

test comparing the 2 treatment groups with respect to response, with site in the model. In a model without site, the sample size was n=234 (117 per treatment group). The model with sites included was originally considered with the following assumptions: 30 sites of varying sizes (6 sites with 1% of the total sample each, 6 with 2%, 6 with 3%, 6 with 4%, 3 with 5%, 1 with 6%, 1 with 8% and 1 with 11%); and varying responder rates among sites (one fixed as having the lowest, and the next lowest having an odds ratio of 1.05 compared to the lowest and so on, until the one with the highest, which has an odds ratio of $[1.05]^{29} \approx 4.12$ compared to the lowest; this variation among sites is perhaps larger variation among sites than one would expect). In the PROC POWER runs, this site effect was specified in fixed order, and the site size was randomly scrambled. In 10 runs, the sample size needed for 90% power ranged from 239 to 242, averaging 240.7. Hence, the final target sample size is taken to be 240. With a sample size of 240, the study will have 80% power to detect a difference if the NAL ER 162 mg responder rate is as low as 41.8%.

To address the concern of the reliability of the estimates of treatment effectiveness from the previous studies, an adaptive mid-course sample size re-estimation procedure will be performed when 50% of the subjects have either completed the Week 14 primary endpoint assessment or terminated from the study early. The data for the re-estimation of sample size will be unblinded to an independent statistician and the sample size may be increased up to the predefined maximum allowable sample size if the conditional power is within the promising zone; therefore, this re-estimation will not inflate the type I error.

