After imputing the missing values, logistic regression will be performed 50 times using imputed datasets. The estimates will be combined using PROC MIANALYZE procedure.

8.6.1.2. Tipping point analysis.

The tipping point analyses is to assess how much the missing data would have to differ from the imputed data that is based on a MAR assumption in order to reverse the conclusions of the trials. This can be done using PROC MIANALYZE. Tipping point analyses are typically used to ensure that missing data imputation does not create false positive inferences.

this time, we do not know if the current study will result in an inference that suggests treatment benefits. The TPA description below describes the derivation for treatment benefit and absence of treatment benefit. The primary decision to be made in the tipping point analysis is determining the value of delta). In this case, we have used the standard deviation of the efficacy measure of the subjects in the treatment group who completed all visits.

Non-monotonic data will be imputed as above. The Monotonic missing data will be the result of subjects dropping out of the study. For the primary endpoint, we are only concerned with responders (decrease ≥ 4 points in the WINRS scale) and non-responders at week 14. So in this case we will be looking at the dropouts in the stable double-blind phase.

Determining the delta for the tipping point analysis would follow the following steps. Impute missing values one visit at a time as above for control subjects; Please refer to the [Appendix](#) for details.

1. Estimate the mean scores and standard deviations (SD) in those who completed all visits;
2. Use the standard deviation of the completers as the initial delta value for the dropouts;
3. If the week 2 value is missing in the original data, then in the TPA, the imputed value for week 2 will be modified by adding the SD of the completer's week 2 value to the imputed value.

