if v4 = . then Imp_v4 = 1; else Imp_v4 = 0;
if v5 = . then Imp_v5 = 1; else Imp_v5 = 0;
run;

proc sort data = control_mi; by trt_imputation_usubjid;
proc sort data = NALER_mi; by trt_imputation_usubjid;
data mi; set NALER_mi control_mi; by trt_imputation_usubjid;
run;
  
```

Imputing values in the monotone missing data using regression.

Visit 3 values are imputed using baseline value and treatment;

Visit 4 values are imputed using baseline, treatment and visit 3 & so on.

```

proc sort data = mi; by _Imputation_;
proc mi data=mi out=mi_reg seed=54321 n impute=1;
by _Imputation_;
var trt01pn base v3 v4 v5;
class trt01pn;
monotone regression;
run;
  
```

1. Tipping Point Analysis – Starts here:

Take each group of dropouts – those who dropped out at v3 & subtracting (or adding) the SD of the completers group for that visit from the imputed value.

Then merge it to the original data set.

Then go to the next set of dropouts.

```

data mi_reg2_Impv3; set mi_reg2;
if Imp_v3 = 1
then do;

  /*Create a macro where this value is replaced by the following: (-.25SD, -0.5SD, -
  0.75stddev, -SD, 0.25SD, 0.5SD, 0.75SD, SD), thus reducing the imputed values by a
  quarter, a half, three-quarter and a whole SD. Then, on the other side add 0.25SD, 0.5SD,
  0.75SD*/

v3 = v3-stdv3;
v4 = v4-stdv4;
v5 = v5-stdv5; (each of these is done only for visits that were imputed in the previous step)
end;
run;
proc sort data = mi_reg2; by _Imputation_usbjid;
proc sort data = mi_reg2_impv3; by _Imputation_usbjid;
data mi_reg4; merge mi_reg2 mi_reg2_impv3; by _Imputation_usbjid;
run;

data mi_reg4_Impv4; set mi_reg4;
if Imp_v4 = 1
then do;
v4 = v4-stdv4;
v5 = v5-stdv5;
end;
run;
proc sort data = mi_reg4; by _Imputation_usbjid;
proc sort data = mi_reg4_impv4; by _Imputation_usbjid;
data mi_reg5; merge mi_reg4 mi_reg4_impv4; by _Imputation_usbjid;
run;

data mi_reg5_Impv5; set mi_reg5;
if Imp_v5 = 1
then do;
v5 = v5-stdv5;
end;
run;
proc sort data = mi_reg5; by _Imputation_usbjid;

```

```

proc sort data = mi_reg5_impv5; by _Imputation_usubjid;
data mi_reg6; merge mi_reg5 mi_reg5_impv5; by _Imputation_usubjid;
run;
  
```

The result of the above steps is a modified horizontal data set with the modified imputed values. Now, proceed as before by converting this to a vertical data set & fitting GENMOD or MIXED.

2. Convert the data set from a horizontal dataset, i.e. one row per subject to a vertical data set, i.e., multiple rows per subject.

```

Data mi_reg1; set mi_reg;

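### The tipping-point analysis runs a fixed list of shifts ending at 1 SD, with no rule to continue until the result reverses or every imputed NAL ER dropout is a non-responder

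*SAP*

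**What the plan says.** SAP 8.6.1.2 states the aim as to "assess how much the missing data would have to differ from the imputed data" under MAR before the trial's conclusion reverses. For the size of the shift it says: "Use the standard deviation of the completers as the initial delta value for the dropouts". Each imputed visit value is then moved once, by that visit's completer SD. Step 4 of the same section changes only the sign. No second value and no stopping rule follow.

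The multipliers appear only in the code comment in SAP Appendix 12.3: "Create a macro where this value is replaced by the following: (-.25SD, -0.5SD", continuing "0.75stddev, -SD, 0.25SD, 0.5SD, 0.75SD, SD), thus reducing the imputed values by a" quarter, a half, three quarters and a whole SD. The comment closes by listing the additions as 0.25, 0.5 and 0.75 SD. A higher WI-NRS means worse itch, so additions are the unfavourable direction for NAL ER. In that direction the list ends at 1 SD and the closing sentence at 0.75 SD.

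The sample code then runs three blocks in sequence, keyed to whether visits 3, 4 and 5 (Weeks 6, 10 and 14) were imputed.

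**The concern.** A tipping-point analysis answers its question in one of two ways. It finds the shift at which significance is lost, or it shows that significance survives the most extreme case. A fixed list does neither if the result is still significant at its last entry and that entry falls short of the extreme. The report would say that the result did not tip and would read as robust, although a somewhat larger shift might remove significance.

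The bound carries extra weight here. Protocol 13.4.6.1 counted a missing Week 14 value as non-response in the primary analysis, whereas SAP 7.4.1 and 8.6 leave it missing under MAR. The tipping-point analysis is the natural place for the non-responder case to reappear.

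**Working it through.** **Inputs from the documents.** SAP 5 gives "responder percentages for placebo and NAL ER of 25% and 45%, respectively"; "Power is set at 90% with a 2-sided significance level of 0.05". Protocol 9.1.1: "Approximately 360 subjects with diagnosed PN will be randomized (1:1"), so 180 per arm. Protocol 13.1 gives TR03 results of 6/18 and 4/22 for all treated, and 6/12 and 4/20 for completers. TR03 dropout was therefore 1 − 12/18 = 33.3% on NAL ER 162 mg and 1 − 20/22 = 9.1% on placebo. The SAP uses 50 imputations.

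**Not in the documents.** They give no expected dropout for this trial and no WI-NRS SD. I assume a normal latent change score, equal SDs for score and change, and a two-group log odds ratio in place of the repeated-measures GENMOD model. Placebo dropout is 9%, imputed under MAR.

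**Check on the plan's figure.** n per arm = [1.96·√(2·0.35·0.65) + 1.2816·√(0.25·0.75 + 0.45·0.55)]² / 0.20² = 117.4, rounded up to 118 (236 in total). SAP 5.2 says: "In a model without site, the sample size was n=234 (117 per treatment group"), and the final target is 240. The figures agree closely.

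**What a shift of k SD leaves.** q(k) = Φ(Φ⁻¹(0.45) − k) = Φ(−0.126 − k). This gives 19.1% at 0.75 SD, 13.0% at 1 SD, 1.7% at 2 SD and 0.1% at 3 SD.

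**Test statistic.** With NAL ER dropout d, the arm's rate is P = (1 − d)·0.45 + d·q. Then z = log OR / √(W + (1 + 1/50)·B), where:

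- W = 1/[180·P(1 − P)] + 1/[180·0.25·0.75]
- B for NAL ER = d²·[q(1 − q)/(180d) + V] / [P(1 − P)]²
- V = φ(x)²·(1 + Φ⁻¹(0.45)²/2) / [180(1 − d)], with x = Φ⁻¹(0.45) − k
- B also includes the same expression for placebo (rate 0.25, dropout 9%, k = 0), which is 0.0029

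**Worked case, d = 25%.**

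- At 1 SD: P = 0.3375 + 0.25·0.130 = 0.370. Log OR = ln(0.370/0.630) − ln(0.25/0.75) = 0.567. W = 0.0238 + 0.0296 and B = 0.0033 + 0.0029, so SE = 0.244, z = 2.32, p = 0.020.
- With every NAL ER dropout a non-responder: P = 0.3375, log OR = 0.424, SE = 0.240, z = 1.77, p = 0.077. The tip is at 1.58 SD.

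| NAL ER dropout | p at 0.75 SD | p at 1 SD | p, all NAL ER dropouts non-responders | Tipping shift |
|---|---|---|---|---|
| 20% | 0.005 | 0.009 | 0.028 | none |
| 25% | 0.010 | 0.020 | 0.077 | 1.58 SD |
| 28% | 0.016 | 0.033 | 0.13 | 1.20 SD |
| 30% | 0.021 | 0.044 | 0.18 | 1.05 SD |
| 33.3% (TR03) | 0.032 | 0.071 | 0.30 | 0.88 SD |

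The band in which a tip exists only beyond 1 SD is about 23–31% with 9% placebo dropout, and starts at 22% if both arms drop out equally. If the score SD is 0.8 to 1.25 times the change SD, the TR03-dropout tip moves between about 1.1 and 0.7 SD.

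**45% read as the all-treated rate.** SAP 5.1 argues it this way. With 50% among completers, 45/50 implies 10% dropout. Placebo completers are 25%/(20/22) = 27.5%. Then z is about 4.1 under MAR, 3.58 at 1 SD and 3.34 (p about 0.0008) at the bound. There is no tipping point.

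**Trial-to-trial variation.** In 1,500 simulated trials per scenario (180 per arm, MAR reading), among those significant under MAR the tip lay only beyond 1 SD in 4% at 10% dropout, 16% at 20%, 24% at 25% and 29% at 33%.

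**The sample code.** After monotone imputation, a subject missing from visit 3 is also flagged at visits 4 and 5. The visit-3 block shifts visits 3, 4 and 5; the visit-4 block shifts 4 and 5 again; the visit-5 block shifts 5 once more. The Week 14 value moves three times (twice for a dropout at visit 4), against the single shift per visit in 8.6.1.2.

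**The case against.** The strongest reply has three parts.

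First, Appendix 12.3 describes itself as guidance rather than exact code, and 8.6.1.2 calls 1 SD the initial delta, which leaves room for more. That is fair, but neither place says what comes next or when to stop, so the choice would be made after unblinding.

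Second, run literally, the code's nominal 1 SD becomes 2 or 3 SD at Week 14 for early dropouts. That leaves 1.7% or 0.1% responders, which is nearly the bound. This also stands as a fact, but it contradicts 8.6.1.2. The reach of the list then depends on which text the programmer follows.

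Third, a reader might infer that, under the trial's own planning values, a tipping point exists and the list stops short of it. The documents do not support that. With 45% as an all-treated rate there is no tipping point, and reporting none would be correct. With 45% as a MAR rate and TR03 dropout, the tip is at 0.88 SD, inside the list. A pooled two-proportion z test at 32% dropout does give p of about 0.045 at 1 SD, but it omits the between-imputation variance that PROC MIANALYZE adds. With that variance p is about 0.06, so the result has already tipped.

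**Conclusion.** The point holds as a gap in method: the list has no stopping rule and, with one shift per visit, does not reach the all-non-responder bound. Whether this would mislead depends on dropout. With 45% v 25% as MAR rates, the early stop is harmless on expected values at NAL ER dropout of about 20% or less. It hides a tip at about 22–31%. At 33% it matters only if the unfavourable side stops at 0.75 SD, as the closing sentence has it (p = 0.032 there, so not tipped). If 45% is all-treated, it is harmless. These figures rest on the assumptions listed with the inputs, above all the assumed dropout and the ratio of the two SDs. The change is worth making before unblinding, but the plan is not shown to give a wrong answer on its own planning figures.

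**What to change.** In SAP 8.6.1.2 and Appendix 12.3, replace the fixed list in the unfavourable direction (added itch) with a loop:

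- Increase the shift for imputed NAL ER values in steps of 0.25 SD until the Week 14 p-value combined over imputations exceeds 0.05, or every imputed NAL ER dropout is a non-responder.
- Report the tipping shift in WI-NRS points and the NAL ER dropout response rate it implies, or state that no tipping point exists.
- Apply one shift per visit, as 8.6.1.2 describes, and rewrite the three sequential blocks so that no value moves more than once.
- Remove the conflict between 0.75 SD and 1 SD as the end of the added shifts.

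The cost is a loop with a stopping condition, more runs of 50 imputed datasets, and possibly a tipping point that looks less favourable than a list that ended early.
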